10.5. Derived and transformed data

The cut-off value is defined by the laboratory before the analysis and is described in the laboratory assays section (Section 5.7.3).

- A seronegative subject is a subject whose antibody concentration/titre is below the assay cut-off.
- A seropositive subject is a subject whose antibody concentration/titre is greater than or equal to the assay cut-off.
- A seroprotected subject is a subject whose antibody concentration/titre is greater than or equal to the level defining clinical protection. The following seroprotection thresholds are applicable:
 - Anti-diphtheria antibody concentrations ≥ 0.1 IU/ml.
 - Anti-tetanus antibody concentrations ≥ 0.1 IU/ml.
 - Anti-poliovirus types 1, 2 and 3 antibody titres ≥ 8 .
 - Anti-PRP antibody concentrations ≥ 0.15 μ g/ml.
- The geometric mean concentrations (GMCs) /geometric mean titres (GMTs) calculations will be performed by taking the anti-log of the mean of the \log_{10} concentration/titre transformations. Antibody concentrations/titres below the cut-off of the assay will be given an arbitrary value of half the cut-off for the purpose of GMC/GMT calculation.
- Handling of missing data:

Immunogenicity

For a given subject and a given immunogenicity measurement, missing or non-evaluable measurements will not be replaced. Therefore, an analysis will exclude subjects with missing or non-evaluable measurements.

Safety/reactogenicity

- For a given subject and the analysis of solicited AEs 3 days post-vaccination, missing or non-evaluable measurements will not be replaced. Therefore the analysis of the solicited AEs based on the Total Vaccinated cohort will include only vaccinated subjects and doses with documented safety data (i.e. symptom screen completed).
- For analysis of unsolicited AEs, such as SAEs or AEs by primary Medical Dictionary for Regulatory Activities (MedDRA) term, and for the analysis of concomitant medications, all vaccinated subjects will be considered. Subjects who did not report the event or the concomitant medication will be considered as subjects without the event or the concomitant medication respectively.

For summaries reporting both solicited and unsolicited AEs, all vaccinated subjects will be considered. Subjects who did not report the event or the concomitant medication will be considered as subjects without the event or the concomitant medication respectively.

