10.8. Analysis of safety

Analysis of safety relative to the primary epoch will include analysis of safety data collected following administration of the three primary doses of study vaccine. Analysis of safety relative to the booster epoch will include analysis of safety data collected following administration of the booster dose of study vaccine. At this second stage, in

order to avoid missing SAEs that have been reported, an SAE summary table including all the events reported during the entire study period will also be generated.

The analysis will be based on the Total vaccinated cohort for both primary and booster epochs. All analyses are descriptive.

- The overall percentage of subjects/doses with at least one local symptom (solicited or unsolicited), with at least one general symptom (solicited or unsolicited) and with any symptom (solicited or unsolicited) during the 4-day (Days 0-3) solicited follow-up period will be tabulated with exact 95% CI [Clopper, 1934] after each vaccine dose and overall primary doses. The same calculations will be done for symptoms (solicited or unsolicited) rated as grade 3 in intensity, for symptoms (solicited or unsolicited) leading to medical advice and for symptoms (solicited or unsolicited) assessed as causally related to vaccination.
- The overall percentage of subjects/doses and of subjects reporting each individual solicited local and general symptom during the 4-day (Days 0-3) solicited follow-up period will be tabulated after each vaccine dose and overall primary doses, with exact 95% CI [Clopper, 1934] after each vaccine dose and overall primary doses. The same calculations will be done for each individual solicited symptom rated as grade 3 in intensity and for each individual solicited symptom assessed as causally related to vaccination.
- Occurrence of fever will be reported per 0.5°C cumulative increments.

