- The verbatim reports of unsolicited AEs will be reviewed by a physician and the signs and symptoms will be coded according to MedDRA. Every verbatim term will be matched with the appropriate Preferred Term. The percentage of subjects with unsolicited AEs occurring within 31-day (Days 0-30) follow-up period after any dose (after primary or booster vaccination) with its exact 95% CI will be tabulated by preferred term. Similar tabulation will be done for unsolicited AEs rated as grade 3, for unsolicited AEs with causal relationship to vaccination and AE(s)/SAE(s) leading to withdrawal from the study.
- The percentage of subjects who receive at least one concomitant medication during the 4-day (Days 0-3) solicited follow-up period and during the entire primary/booster epoch will be tabulated (with exact 95% CI after each vaccine dose and overall).
- Any large injection site reaction (defined as a swelling with a diameter > 50 mm, noticeable diffuse swelling or noticeable increase in limb circumference) after booster vaccination will be described in detail.

SAE(s) will be described in detail.

Handling of missing data:

- For a given subject and the analysis of solicited symptoms four days post-vaccination, missing or non-evaluable measurements will not be replaced. Therefore the analysis of the solicited symptoms based on the TVC will include only vaccinated subjects and doses with documented safety data (i.e., symptom screen completed).
- For analysis of unsolicited AEs, such as SAEs or AEs by primary Medical Dictionary for Regulatory Activities (MedDRA) term, and for the analysis of concomitant medications, all vaccinated subjects will be considered. Subjects, who do not report the event or the concomitant medication, will be considered as subjects without the event or the concomitant medication, respectively.
- For summaries reporting both solicited symptoms and unsolicited AEs, all vaccinated subjects will be considered. Subjects, who do not report the event or the concomitant medication, will be considered as subjects without the event or the concomitant medication, respectively.

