11.2.2. Dose number

- The study dose number is defined in reference to the number of study visits at which vaccination occurred. More specifically dose 1 refers to all vaccines administered at the first vaccination visit while dose 2 corresponds to all vaccinations administered at the second vaccination visit even if this is the first time a product is administered to the subject.
- Relative dose: the relative dose for an event (AE, medication, vaccination) is the most recent study dose given before an event. In case the event takes place on the day a study dose is given, the related dose will be that of the study dose, even if the event actually took place before vaccination. For instance, if an adverse event begins on the day of the study vaccination but prior to administration of the vaccine, it will be assigned to this dose. In case a study dose is not administered and an event occurs after the subsequent study dose (eg 3rd study dose), the relative dose of the event will be study dose associated to the subsequent study dose (eg dose 3).
- The number of doses for a product is the number of time the product was administered to a subject.
- The incidence per dose is the number of vaccination visits at which an event was reported among all vaccination visits.

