11.2.5. Safety

For analysis of solicited, unsolicited adverse events (such as serious adverse events or adverse events by primary MedDRA term) and for the analysis of concomitant medications, all vaccinated subjects will be considered. Subjects who did not report the event or the concomitant medication will be considered as subjects without the event or the concomitant medication respectively.

The following rules will be used for the analysis of solicited symptoms:

- Subject who didn't document the presence or absence of a solicited symptom after one dose will be considered not having that symptom after that dose in the analysis done on "administered dose"
- Subjects who documented the absence of a solicited symptom after one dose will be considered not having that symptom after that dose.
- Subjects who documented the presence of a solicited symptom and fully or partially recorded daily measurement over the solicited period will be included in the summaries at that dose and classified according to their maximum observed daily recording over the solicited period.
- Subjects who documented the presence of a solicited symptom after one dose without having recorded any daily measurement will be considered as having that symptom after that dose (at the lowest intensity).
- Intensity of the following solicited AEs will be assessed as described in [Table 4](#) and below

Table 4 Intensity scales to be used by the parent(s)/LAR(s) for solicited symptoms during the solicited follow-up period

Infant		
Adverse Event	Intensity grade	Parameter
Pain at injection site	0	None
	1	Mild: Minor reaction to touch
	2	Moderate: Cries/protests on touch
	3	Severe: Cries when limb is moved/spontaneously painful
Redness at injection site		Record greatest surface diameter in mm
Swelling at injection site		Record greatest surface diameter in mm
Fever*		Record temperature in °C/°F
Irritability/Fussiness	0	Behaviour as usual
	1	Mild: Crying more than usual/no effect on normal activity
	2	Moderate: Crying more than usual/interferes with normal activity
	3	Severe: Crying that cannot be comforted/prevents normal activity
Drowsiness	0	Behaviour as usual
	1	Mild: Drowsiness easily tolerated
	2	Moderate: Drowsiness that interferes with normal activity
	3	Severe: Drowsiness that prevents normal activity
Loss of appetite	0	Appetite as usual
	1	Mild: Eating less than usual/no effect on normal activity
	2	Moderate: Eating less than usual/interferes with normal activity

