		Any symptom			General symptoms			Local symptoms								
		95% CI		95% CI		95% CI		95% CI		95% CI		95% CI		95% CI		
	Group	N	n	%	LL	UL	N	n	%	LL	UL	N	n	%	LL	UL
Dose 2	Combo group	224	18	8.0	4.8	12.4	224	7	3.1	1.3	6.3	224	12	5.4	2.8	9.2
	Control group	227	15	6.6	3.7	10.7	227	6	2.6	1.0	5.7	227	11	4.8	2.4	8.5
Dose 4	Combo group	224	29	12.9	8.8	18.1	224	6	2.7	1.0	5.7	224	26	11.6	7.7	16.5
	Control group	227	29	12.8	8.7	17.8	227	9	4.0	1.8	7.4	227	22	9.7	6.2	14.3
Dose 6	Combo group	224	25	11.2	7.4	16.0	224	8	3.6	1.6	6.9	224	18	8.0	4.8	12.4
	Control group	227	19	8.4	5.1	12.8	227	2	0.9	0.1	3.1	227	18	7.9	4.8	12.2
Overall/dose	Combo group	672	72	10.7	8.5	13.3	672	21	3.1	1.9	4.7	672	56	8.3	6.4	10.7
	Control group	681	63	9.3	7.2	11.7	681	17	2.5	1.5	4.0	681	51	7.5	5.6	9.7
Overall/subject	Combo group	224	60	26.8	21.1	33.1	224	21	9.4	5.9	14.0	224	44	19.6	14.7	25.5
	Control group	227	47	20.7	15.6	26.6	227	14	6.2	3.4	10.1	227	39	17.2	12.5	22.7

Combo group = Subjects received DTPa-IPV/Hib vaccine as a single injection at 2, 4 and 6 months of age

Control group = Subjects received DTPa-IPV and Hib vaccines at different injection sites at 2, 4 and 6 months of age

For each dose and overall/subject:

N = number of subjects with at least one administered dose

n/% = number/percentage of subjects presenting at least one type of symptom whatever the study vaccine administered

For overall/dose:

N = number of administered doses

n/% = number/percentage of doses followed by at least one type of symptom whatever the study vaccine administered

95% CI = exact 95% confidence interval, LL = Lower Limit, UL = Upper Limit

Dose 2, 4 and 6 are the doses where subjects has received study vaccine - DTPa-IPV/Hib vaccine in Combo group and DTPa-IPV and Hib in Control group

CONFIDENTIAL
 116194 [DTPa-IPV (INFANRIX-IPV)-061]
 Statistical Analysis Plan Amendment 2 Final

**Template 13 Incidence of solicited local symptoms reported during the 4-day
(Days 0-3) period after vaccination following each dose and overall
(Total vaccinated cohort)**

Symptom	Type	Combo group					Control group				
					95 % CI					95 % CI	
		N	n	%	LL	UL	N	n	%	LL	UL
Dose 2											
Pain	All	224	108	48.2	41.5	55.0	227	113	49.8	43.1	56.5
	Grade 3	224	5	2.2	0.7	5.1	227	8	3.5	1.5	6.8
Redness (mm)	All	224	133	59.4	52.6	65.9	227	119	52.4	45.7	59.1
	>20	224	4	1.8	0.5	4.5	227	3	1.3	0.3	3.8
Swelling (mm)	All	224	65	29.0	23.2	35.4	227	64	28.2	22.4	34.5
	>20	224	5	2.2	0.7	5.1	227	2	0.9	0.1	3.1
Dose 4											

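### The Days 0-3 combined symptom tables count a dose without a completed symptom screen as free of solicited symptoms, so the combined rates are understated to the extent that diary cards are missing

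*Protocol*

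**What the plan says.** Protocol 10.5 has two rules for missing safety data that bear on solicited symptoms.

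- **Solicited symptoms alone.** Missing measurements are not replaced: "Therefore the analysis of the solicited AEs based on the Total Vaccinated cohort will include only vaccinated subjects and doses with documented safety data".
- **Solicited and unsolicited events together.** "For summaries reporting both solicited and unsolicited AEs, all vaccinated subjects will be considered", and "Subjects who did not report the event or the concomitant medication will be considered as subjects without the event".

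SAP 6.4.1 keeps both rules; for the second it says "For summaries reporting both solicited symptoms and unsolicited AEs, all vaccinated subjects will be considered".

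The first analysis listed in Protocol 10.8 and SAP 6.4.1 falls under the second rule. It is the percentage of subjects and doses with a local symptom, with a general symptom, and "with any symptom (solicited or unsolicited) during the 4-day (Days 0-3) solicited follow-up period will be tabulated with exact 95% CI". The same calculation is repeated for grade 3, medically attended and causally related symptoms.

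The SAP annexes show the same split. Section 11.2.5 says that a subject who did not document "the presence or absence of a solicited symptom after one dose will be considered not having that symptom after that dose", and limits this to the analysis on administered doses. Section 11.2.2 defines per-dose incidence generally: "The incidence per dose is the number of vaccination visits at which an event was reported among all vaccination visits". The mock combined table (Annex 3, Template 12) has "N = number of subjects with at least one administered dose", whereas the mock table of individual local symptoms (Template 13) uses documented doses.

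SAP 11.2.5 is not consistent within itself. Its opening sentence applies the all-vaccinated rule to solicited events as well. Its later denominator table uses documented subjects and doses for solicited general symptoms, and has no row for combined summaries.

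**The concern.** Treating no report as no event is a normal convention for unsolicited events and SAEs, which are recorded when they occur. Solicited symptoms are different: they are collected on a diary card, and a card that does not come back leaves them unknown. In Days 0-3 the combined tables can be expected to consist largely of solicited symptoms, so the convention is applied mainly to data for which it is least suited.

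Coding unknown as absent can only lower the combined rate or leave it unchanged, relative to the doses that were documented. The trial has one group and no control, so no comparator offsets the shift. The reported percentage and its exact confidence interval are what a reader will take from the table. Two tables on the same children and the same four days would also rest on different denominators, with no reason given.

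**Working it through.** **Inputs**
- Planned enrolment 235 (Protocol 10.3). The plan's figure reproduces: 200 / 0.85 = 235.3, and 235 x 0.85 = 199.75, about 200.
- Interval method: exact Clopper-Pearson (Protocol 10.8, SAP 11.1). It reproduces all nine rows of Protocol Table 16, for example 190/200 gives 91.0 to 97.6.
- Share of doses without a completed symptom screen, m: not given for this study, so an assumption. The only return rates in the file are 99.3% to 100% (SAP Template 11). They come from another study, since SAP section 13 says the templates were copied.
- Combined rate among documented doses, p: assumed 70%.

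**Formula.** Let u be the share of doses without a sheet that still have a recorded unsolicited event with onset in Days 0-3. Then

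reported rate = p(1 - m) + u m.

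With u = 0 this is p(1 - m), the largest understatement for a given m.

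**Results for one vaccination, 235 doses, u = 0**

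| Sheets missing | Documented doses | All administered doses |
|---|---|---|
| 2 (0.9%) | 163/233 = 70.0% | 163/235 = 69.4% |
| 12 (5.1%) | 156/223 = 70.0% (63.5 to 75.9) | 156/235 = 66.4% (60.0 to 72.4) |
| 23 (9.8%) | 148/212 = 69.8% (63.1 to 75.9) | 148/235 = 63.0% (56.5 to 69.2) |

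In the last row the documented-dose estimate, 69.8%, lies just above the upper limit of the all-dose interval, 69.2%.

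For a grade 3 rate near 10.7% (72/672 in Template 12, another study's data), 12 missing sheets give 24/235 = 10.2% instead of 24/223 = 10.8%.

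**Can the combined rate fall below one of its components?** The component is computed on documented doses, so this needs p_any(1 - m) < p_comp, that is m > 1 - p_comp/p_any.
- 70% any symptom against 65% for one symptom: m > 1 - 65/70 = 7.1%.
- 60% against 58.3%: m > 1 - 58.3/60 = 2.8%. The threshold is this low only when one symptom makes up nearly the whole composite.
- Grade 3, with Template 12 and 13 counts (56 local, 72 any, 38 redness above 20 mm): m > 1 - 38/56 = 32% for local, and m > 1 - 38/72 = 47% for any.

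These figures are per dose. In the per-subject summary over the three primary doses, a child with one missing card stays in both denominators, so the effect there does not equal the share of missing cards.

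**The case against.** The case for leaving the rule alone has several sound parts.

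- **The endpoint tables are not affected under SAP 6.4.1.** The secondary endpoint is the occurrence of solicited symptoms, and the individual-symptom tables already use documented doses. The combined table is an added summary. This stands.
- **Card loss may be very small.** Unreturned cards are pursued by telephone or other means (Protocol 5.6.15), parents are actively questioned (8.2.3.1), and a compliance template exists. This also stands, and at 99-100% return nothing of substance changes.
- **Documented doses are not the truth either.** If parents of symptom-free infants return fewer cards, the documented-dose rate is too high. The proportional result therefore needs missing cards to be unrelated to symptoms.
- **A dose without a sheet is not always counted as event-free.** It counts if an unsolicited event in Days 0-3 was recorded. Replacing the denominator outright would remove such events, SAEs included, from the combined tables. This is a good reason to add a version and not to substitute one.

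The Annex 3 templates are weak evidence by themselves, because SAP section 13 calls their titles and footnotes illustrative. The point rests on Protocol 10.5 and SAP 6.4.1.

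Three stronger readings are tempting. A reader might infer that the protocol and SAP disagree on combined summaries; they state the same rule. A reader might infer that reactogenicity will be materially understated; no document gives a card-loss figure to support that. A reader might infer that any composite, grade 3 included, could fall below its own component; the thresholds above make that unlikely for grade 3.

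**Conclusion.** The point holds as one of missing-data handling in the combined Days 0-3 tables. The rule is explicit in both documents, its direction relative to the documented data is certain, and neither document explains why the same missing card is treated in two ways.

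Its size is conditional. If missing cards are unrelated to symptoms and no unsolicited events are recorded for the doses concerned, the per-dose relative understatement equals the share of missing cards. On an assumed 70% rate that means about 66% at 5% missing and 63% at 10%, and next to nothing at 99-100% return. A composite below its component is possible for all-grade symptoms with one dominant symptom, above about 7% card loss for 70% against 65%. All analyses are descriptive, so no hypothesis test is affected.

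Separately, the opening sentence of SAP 11.2.5 conflicts with SAP 6.4.1 and with the denominator table in 11.2.5. Read literally, it would carry the all-vaccinated rule into the individual solicited tables.

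**What to change.** 1. In SAP 6.4.1 and 11.2.5, specify that the Days 0-3 combined tables (any, local, general; all grades, grade 3, medically attended, causally related) are also produced with N equal to subjects or doses with a completed symptom screen. Present them beside the all-vaccinated version and the compliance table. Unsolicited events and SAEs recorded without a sheet then remain visible.
2. Remove solicited events from the opening sentence of SAP 11.2.5, or limit it to the all-vaccinated combined summaries, so that it agrees with SAP 6.4.1. Add rows for both versions of the combined summaries to the denominator table.
3. Leave the combined MedDRA summary (Template 22) with its single N per group. Separate denominators for solicited and unsolicited terms would not fit its row for at least one symptom.

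The cost is SAP wording, one denominator flag and one extra set of tables. No new data are needed.

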10.6. Analysis of demographics

The analysis of demographics will be performed separately for each epoch:

- The distribution of subjects enrolled among the study centers will be tabulated.
- The number of subjects who withdraw from the study will be tabulated according to the reason for drop-out.
- The deviations from specifications for age and intervals between study visits will be tabulated.

The median, mean, range and standard deviation of age (in weeks) at each vaccine dose will be computed. The median, mean and standard deviation of height in centimeter (cm) and weight in kilograms (kg) at Visit 1 will be computed. The Body Mass Index (BMI) at Visit 1 will also be computed as weight (in kg) / height² (in meters). The gender composition and geographic ancestry will be presented.

10.7. Analysis of immunogenicity

The analysis of immunogenicity will be performed separately for each epoch.

The primary analysis will be based on the ATP cohort for analysis of immunogenicity for both primary and booster epochs. If the percentage of enrolled subjects excluded from this ATP cohort is more than 5%, a second analysis based on the Total vaccinated cohort will be performed on both primary and booster epochs to complement the ATP analysis. All analyses are descriptive.

Where appropriate, at each time-point that a blood-sample result is available:

- Seroprotection rates against diphtheria toxoid, tetanus toxoid, PRP antigen and poliovirus types 1, 2 and 3 antigens (with exact 95% CI [Clopper, 1934]) will be calculated.
- Seropositivity rates against PT, FHA and PRN antigens (with exact 95% CI [Clopper, 1934]) will be calculated.
- GMCs/GMTs with 95% CI will be tabulated for antibodies against each antigen.

The distribution of antibody concentrations/titres for each antigen will be displayed using reverse cumulative distribution curves (RCCs).

10.8. Analysis of safety

Analysis of safety relative to the primary epoch will include analysis of safety data collected following administration of the three primary doses of study vaccine. Analysis of safety relative to the booster epoch will include analysis of safety data collected following administration of the booster dose of study vaccine. At this second stage, in

order to avoid missing SAEs that have been reported, an SAE summary table including all the events reported during the entire study period will also be generated.

The analysis will be based on the Total vaccinated cohort for both primary and booster epochs. All analyses are descriptive.

- The overall percentage of subjects/doses with at least one local symptom (solicited or unsolicited), with at least one general symptom (solicited or unsolicited) and with any symptom (solicited or unsolicited) during the 4-day (Days 0-3) solicited follow-up period will be tabulated with exact 95% CI [Clopper, 1934] after each vaccine dose and overall primary doses. The same calculations will be done for symptoms (solicited or unsolicited) rated as grade 3 in intensity, for symptoms (solicited or unsolicited) leading to medical advice and for symptoms (solicited or unsolicited) assessed as causally related to vaccination.
- The overall percentage of subjects/doses and of subjects reporting each individual solicited local and general symptom during the 4-day (Days 0-3) solicited follow-up period will be tabulated after each vaccine dose and overall primary doses, with exact 95% CI [Clopper, 1934] after each vaccine dose and overall primary doses. The same calculations will be done for each individual solicited symptom rated as grade 3 in intensity and for each individual solicited symptom assessed as causally related to vaccination.
- Occurrence of fever will be reported per 0.5°C cumulative increments.
- The verbatim reports of unsolicited AEs will be reviewed by a physician and the signs and symptoms will be coded according to MedDRA. Every verbatim term will be matched with the appropriate Preferred Term. The percentage of subjects with unsolicited AEs occurring within 31-day (Days 0-30) follow-up period after any dose (after primary or booster vaccination) with its exact 95% CI [Clopper, 1934] will be tabulated by preferred term. Similar tabulation will be done for unsolicited AEs rated as grade 3, for unsolicited AEs with causal relationship to vaccination and AE(s)/SAE(s) leading to withdrawal from the study.
- The percentage of subjects who receive at least one concomitant medication during the 4-day (Days 0-3) solicited follow-up period and during the entire primary/booster epoch will be tabulated (with exact 95% CI [Clopper, 1934]) after each vaccine dose and overall.
- Any large injection site reaction (defined as a swelling with a diameter > 50 mm, noticeable diffuse swelling or noticeable increase in limb circumference) after booster vaccination will be described in detail.
- SAE(s) will be described in detail.

